Biomarker plasma samples: samples of plasma and serum will be stored at baseline, 0, 12, 24 and 36 months according to the study Sample Handling Protocol. In total, we will withdraw 7 mls serum at each of these time-points (stored in five aliquots of around 0.5 mls each), and will repeat this procedure for 7 mls EDTA plasma; thus, in total, we will retain 10 aliquots (5 serum, 5 plasma) of samples for biomarker tests. All will stored at -80°C for later transport to the central laboratory in Glasgow. Lipids, hsCRP, t-PA, sE-

selectin, sICAM-1 and apoproteins will initially be measured on two such aliquots. hsCRP and apoproteins will be measured on automated platforms in NHS Glasgow laboratories. Other assays will be run using established ELISAs with all samples run at the same time to minimise variability. Eight aliquots at each timepoint will be retained for future assays of interest as prioritised by the Steering Committee. Transport on to other laboratories will be covered by separate Material Transfer Agreements. These will include markers of endothelial function (t-PA, sE-selectin, sICAM-1), vitamin B12 status (homocysteine, holotranscobalamin-II, S-adenosylmethionine), and Advanced Glycosylation End-products. As novel genes are currently being identified determining therapeutic response to metformin, we will also retain buffy coat for later DNA extraction.

Endothelial function: will be measured using ENDOPAT (Itamar ®) as Reactive Hyperaemia Peripheral Arterial Tonometry (RH-PAT), a non-invasive measurement of peripheral microvascular endothelial function using changes in digital pulse volume during reactive hyperaemia, at 0, 12 and 36 months (in approximately 400 of the 500 patients i.e. in 80% of the study centres). This method has been validated in children with T1DM in whom it has been shown to detect endothelial dysfunction.⁴⁷ As Raynaud's phenomenon and treatment with α -blockers are contraindications to ENDOPAT, any affected individuals will be excluded from these assessments.

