We intend to analyse IMT data using repeated measures regression analysis assuming a linear progression in IMT measurements. We expect a mean progression of 0.044mm over 3 years (in the control arm) and a standard deviation (SD) for progression of 0.05 mm; therefore a final sample size of 200 per treatment arm will provide 90% power (at 5% significance level) to detect a difference of at least one third of an SD (0.0167mm) in 3 year progression of averaged mean cIMT between treatment arms - an effect size more conservative than reported for acarbose, statins, and TZDs on cIMT.

We therefore aim to recruit 500 patients (allowing for around 20-25% treatment discontinuation/ drop-out) and making the very conservative assumption that all those discontinuing treatment/ and withdrawing consent would not even have one follow up measurement (in reality this may occur after one or more follow up cIMT measurements so power will be more than this estimate).

Rates of progression and variation of common carotid artery IMT vary widely between different studies and data from T1DM patients, other than the patients in DCCT/EDIC who are younger than this trial participants, are sparse. Our estimate of progression rate over three years (0.044 mm) is at the lower boundary of that reported by Bots in a meta-analysis of cIMT progression rates of control groups (almost all non-diabetic) from published RCTs.⁵⁰ In that analysis the annual rate of change in mean cIMT was 0.0176 mm (95% CI, 0.0149 to 0.0203). Whilst many of the control group participants in this pooled analysis were not on statins (in contrast to many REMOVAL participants with T1DM) almost all were non-diabetic so that their progression rate would be expected to be lower than in diabetes.

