Other endpoints: The sample size for the study is based on the primary endpoint as described above. This sample size also yields 90% power at 5% significance level to detect differences of approximately 0.3 SD in continuous outcomes i.e. lipid, metabolic and endothelial function parameter changes from baseline at follow up. To put this into context, in the largest trial of metformin in T1DM to date the reported effects on LDL-C were considerably larger than this at (0.46 SD) so that we have ample power to replicate and refine the precision of this treatment effect. For other endpoints we acknowledge that power is lower but emphasize that the sample size is appropriately based on the primary endpoint, and that we are stating *a priori* that we will consider a change in two of the seven secondary endpoints to be clinically meaningful. Thus, for retinopathy progression, based on recent data from the Wisconsin Epidemiologic Study of Diabetic Retinopathy (Co-applicant [name]) we expect three year two-step progression in categorical ETDRS retinopathy stage to be 13.7%. Assuming follow-up retinal photographs in 400 participants, treatment with metformin would have to be associated with a hazard ratio of 0.40 to have 80% power to declare significance for this specific secondary endpoint (at $p < 0.05$). Given the relatively low marginal cost of acquiring the retinal photographs, many of which will be captured from routine screening, we believe incorporation of this endpoint in the study is an opportunity to acquire at least a useful point estimate for likely effect size (albeit with wide confidence intervals). This may be

useful in assessing the statistical power of any future retinopathy intervention trials with metformin.

e) Feasibility of achieving required sample size

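### Endothelial function is included in the claim of 90% power at about 0.3 SD, although only about 400 of the 500 participants are measured; on the claim's own simple basis its power is 74–77% at 0.30 SD after the planned losses

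*Protocol*

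**What the plan says.** Protocol section 6(d) sizes the trial on cIMT: "a final sample size of 200 per treatment arm will provide 90% power (at 5% significance level"). It recruits 500, "allowing for around 20-25% treatment discontinuation/ drop-out", while "making the very conservative assumption that all those discontinuing treatment/ and withdrawing consent would not even have one follow up measurement".

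Under the other endpoints, the same section states: "This sample size also yields 90% power at 5% significance level to detect differences of approximately 0.3 SD in continuous outcomes". It then lists what this covers: "lipid, metabolic and endothelial function parameter changes from baseline at follow up". No allowance is made for an outcome that is not measured in everyone.

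Section 6(b) restricts the endothelial measurement (ENDOPAT, at 0, 12 and 36 months). It is done "in approximately 400 of the 500 patients i.e. in 80% of the study centres", and people with Raynaud's phenomenon or taking alpha-blockers are left out. Protocol section 5 and the footnote in SAP 2.4.2 both confirm that only some centres take the measurement.

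SAP 1.4 repeats the power statement for cIMT only. SAP 2.4.2 analyses continuous secondary outcomes with a repeated-measures model on change from baseline. That model adjusts for the baseline level and tests the main effect of treatment across visits.

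**The concern.** The 90% sentence treats endothelial function as if it had the same number of participants as LDL cholesterol, HbA1c or weight. By the protocol's own account it has about a fifth fewer, before any loss to follow-up.

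Endothelial function is one of the secondary outcomes counted in the rule that significant improvement in two or more is clinically meaningful (Protocol section 5; SAP 2.4.2). Section 6(d) is also the only place where either document gives power for this outcome. A null endothelial result could therefore be read against a sensitivity that the stated numbers do not support.

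**Working it through.** **Inputs**
- Effect of about 0.3 SD, 90% power, 5% significance (Protocol 6(d)). Sidedness is not stated, so two-sided is taken and checked below.
- 500 recruited, 20–25% loss, 200 per arm in the final sample (Protocol 6(d)). Equal arms.
- About 400 of 500 with endothelial measurement (Protocol 6(b)).

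**Formulas** (normal approximation, n per arm, effect d in SD units of change)
- Power = Φ(d·√(n/2) − 1.96)
- Difference detectable with 90% power = (1.960 + 1.2816)·√(2/n) = 3.2416·√(2/n)

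**Reproducing the plan.** For cIMT at one third of an SD, n = 2 × (3.2416 ÷ 0.3333)² ≈ 190 per arm, and 200 per arm gives 91.5%. Two-sided 5% therefore fits the plan's primary calculation. For the secondary claim:
- 250 per arm (all 500, no loss), d = 0.30: Φ(0.30 × √125 − 1.96) = 91.8%.
- 200 per arm, d = 0.30: Φ(0.30 × √100 − 1.96) = Φ(1.04) = 85.1%.
- 200 per arm, 90% power: d = 3.2416 × √(2/200) = 0.324, which rounds to 0.3.
- 90% at exactly 0.30 SD needs 2 × (3.2416 ÷ 0.30)² ≈ 234 per arm.

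So the sentence is recoverable for outcomes measured in everyone, either with no losses or by reading the effect as 0.324 SD.

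**Endothelial function.** 400 × 0.80 = 320 and 400 × 0.75 = 300, or 160 and 150 per arm.

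| Per arm | Situation | Power at 0.30 SD | Power at 0.324 SD | Detectable at 90% |
|---|---|---|---|---|
| 200 | subset, no losses | 85.1% | 90% | 0.324 SD |
| 160 | subset, 20% loss | 76.5% | 82.6% | 0.362 SD |
| 150 | subset, 25% loss | 73.8% | 80.2% | 0.374 SD |

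The exclusions for Raynaud's phenomenon and alpha-blockers lower these numbers further, by an amount the documents do not give. A t-based calculation differs by less than half a point.

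**Splitting the gap at 0.30 SD.** With 20% loss, power is 85.1% in the full sample (200 per arm) and 76.5% in the subset (160). With 25% loss, it is 82.8% (187.5 per arm) and 73.8% (150). The subset costs about 9 points in each case. The remainder is the difference between 90% and 83–85%, and it applies to every listed outcome.

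**Effect of the SAP model.** The documents give no between-visit correlation. Assume a common correlation r and equal variances at baseline, month 12 and month 36, with both follow-up visits observed. Averaging the two visits and adjusting for baseline then multiplies the variance of a single change by (1 + 2r)/4, so n is divided by that factor.
- r = 0.3, factor 0.40: 150–160 per arm acts like 375–400; power 98–99%.
- r = 0.5, factor 0.50: acts like 300–320; power 96–97%.
- r = 0.7, factor 0.60: acts like 250–267; power 92–93%.
- r = 0.9, factor 0.70: acts like 214–229; power 87–89%.

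**The case against.** The strongest reply is that 74–77% describes an unadjusted single-visit comparison, which is not the test in SAP 2.4.2. That stands. A reader might infer that the planned subset cannot reach 90% under any analysis, and the documents do not support this: for an assumed r of 0.3 to 0.7 the specified model gives about 92–99%. But the protocol states its 90% in terms of changes from baseline, with no correlation and no claimed gain from the model. Any such gain goes to the other continuous outcomes too, so the fifth fewer participants remains unacknowledged.

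A reader might also blame the whole fall from 90% on the subset. That goes too far. At exactly 0.30 SD the full 200 per arm already gives 85%, and the protocol does say approximately.

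The loss allowance is a conservative one, as the protocol says. Follow-up continues after treatment stops where possible (section 7.3(j)), and month-12 data from people lost later still count. This also stands, but with no losses at all the subset gives 85% at 0.30 SD.

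Three textual defences are weaker.
- Section 6(d) concedes lower power for other endpoints, but this comes after the list that names endothelial function and leads into retinopathy.
- The figure of 400 might be a number after losses, but it is tied to 80% of centres and to the 500, so it is a share of those enrolled.
- The phrase might mean the blood markers, but section 5 makes those tertiary, and endothelial function in some centres is the secondary endpoint.

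Appendix 6 implies 379 + 50 = 429 randomised. With 80% measured and 20–25% lost, that is about 129–137 per arm and 67–70% power on the simple basis. This is only a side note, since the quoted claim is a planning statement for 500.

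**Conclusion.** The point holds as an error in a stated power figure for one secondary outcome. It rests on two-sided 5% testing, equal arms, 400 of 500 measured and the plan's full 20–25% loss. Only the line with no losses and an effect read as 0.324 SD reaches 90% on the simple basis.

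It does not show that the specified analysis is underpowered, because that depends on correlations the documents leave out. The primary sample size is untouched. The rule on two or more secondary outcomes uses no power figure, and the SAP will report an estimate with a 95% confidence interval. What is at stake is therefore how a null endothelial result is interpreted.

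**What to change.** Take endothelial function out of the 90%/0.3 SD sentence in Protocol section 6(d) and give it its own line, for example:

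> Endothelial function is measured in about 80% of participants, leaving about 150–160 per arm after losses. On an unadjusted single-visit comparison of change from baseline, this gives 90% power for about 0.37 SD and about 75% power for 0.30 SD. Power is higher with the baseline-adjusted repeated-measures model, depending on the between-visit correlation.

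For the other continuous outcomes, state the detectable difference as about 0.32 SD at 200 per arm, so that both lines use the same basis. If the team wants to rely on the gain from the SAP model, it should state the assumed correlation and apply it to all continuous outcomes.

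The cost is a sentence or two and a less favourable figure. No participants, visits or analyses change.

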7. STUDY POPULATION

7.1 Inclusion Criteria:

1. Type 1 diabetes for five years or more*
2. age ≥ 40 years
3. $7.0 \leq \text{HbA1c} < 10.0\%$ (53-86 mmol/mol)

*defined as diagnosis below age 40 years AND insulin use within 1 year of diagnosis

AND three or more of the following ten CVD risk factors:

- (i) BMI $> 27 \text{ kg/m}^2$
- (ii) current HbA1c $> 8.0\%$ (64 mmol/mol)
- (iii) known CVD/ peripheral vascular disease

- (iv) current smoker
- (v) estimated glomerular filtration rate < 90 ml/min per 1.73 m² (MDRD equation)
- (vi) confirmed micro- or macroalbuminuria [according to local assays and reference ranges - see Appendix 5]
- (vii) hypertension (BP ≥ 140/ 90 mmHg or established on antihypertensive treatment)
- (viii) dyslipidaemia:
 - total cholesterol ≥ 5.0 mmol/L (200 mg/dL);
 - OR HDL cholesterol < 1.2 mmol/L (46 mg/dL) [men] or < 1.3 mmol/L (50 mg/dL) [women];
 - OR triglycerides ≥ 1.7 mmol/L (150 mg/dL); or established on lipid-lowering treatment
- (ix) strong family history of CVD (at least one parent, biological aunt/ uncle, or sibling with myocardial infarction, coronary artery bypass graft or stroke aged < 60 years)
- (x) duration of diabetes > 20 years.

7.2 Exclusion Criteria:

- (i) Women of childbearing age (i.e. continuing menstrual cycle) not using effective contraception – see Appendix 4.
- (ii) Pregnancy and/or lactation; planning to get pregnant or not using effective contraception
- (iii) Patients with Acute Coronary Syndrome or Stroke/ Transient Ischaemic Attack within the last three months
- (iv) Symptomatic angina on mild or moderate exertion
- (v) Stage 3 or 4 heart failure defined according to the NYHA criteria
- (vi) Estimated glomerular filtration rate < 45 ml/min/1.73m² (MDRD)
- (vi) Contraindications to metformin
 - hepatic impairment (ALT > 3.0 times ULN)
 - known hypersensitivity to metformin
 - acute illness [dehydration, severe infection, shock, acute cardiac failure]
 - suspected tissue hypoxia
- (vii) Metformin treatment for more than three months within last two years
- (viii) Anaemia (haemoglobin < 10.0 g/dL)
- (ix) Ongoing treatment with oral steroids, pramlintide or GLP-1 agonist therapy

- (x) Hypoglycaemia unawareness confirmed as significant by site Principal Investigator
- (xi) Impaired cognitive function/ unable to give informed consent
- (xii) Previous carotid surgery or inability to capture adequate carotid images
- (xiii) Gastroparesis (on gastric emptying studies) confirmed as significant by site Principal Investigator OR more than two hospital admissions with unexplained vomiting in last year
- (xiv) history of biochemically-confirmed acidosis (with lactate > 5.0 mmol/L)
- (xv) Any coexistent life-threatening condition including diagnosis of cancer within prior two years
- (xvi) history of alcohol problem or drug abuse
- (xvii) diabetes other than type 1 diabetes (e.g. secondary to pancreatitis, pancreatectomy or primary pancreatic disease)
- (xviii) Involvement in a clinical trial involving an investigational medicinal product within the last six months

7.3 Identification of participants and Informed Consent.

a) Pre-screening: Procedures may vary between sites, but all have systems in place for identifying potentially eligible participants in secondary and tertiary care. In many sites, participating investigators will systematically review their clinical record systems for potentially eligible patients and invite them to specific screening visits. In other sites, clinical visit lists will be pre-reviewed in order that potentially eligible individuals can be sent an information sheet by post one week before their routine scheduled review visit. Eligibility criteria of those indicating agreement to be approached will then be checked at the routine visit, and the information sheet and study procedures explained. Potential participants will be given a Patient Information Sheet and an Expression of Interest Form (with prepaid envelope) at this time and will be asked for permission to contact again to discuss further and (if appropriate) arrange a screening visit

b) Screening: A separate non-fasting visit will then be arranged within two weeks at which potential participants will have further time to discuss with the study nurse and doctor. Eligibility criteria will be checked by the study doctor and a research nurse. Risks and side-effects of the active trial medication will be explained. Metformin is long established in clinical practice and has a good safety profile. The main side effects are gastrointestinal disturbances that are dose dependent see below. The procedures for management of hypoglycaemia will be discussed: (http://www.sdrn.org.uk/sites/default/files/sop27_managementofhypoglycaemia.pdf).

c) Pregnancy: Women of childbearing age will be asked about pregnancy status and contraceptive usage and a urine pregnancy test will be conducted (following informed consent – see below – and prior to entering the Run-In Period). There have been

several recent trials of metformin use in pregnancy, especially for treatment of gestational diabetes mellitus. Systematic review of these trials concludes no adverse effects of metformin as compared with insulin therapy.^{51,52} Nonetheless in this trial we will not recruit those wanting to become pregnant and will discontinue study drug in women who become pregnant. All such pregnancies will be notified to the pharmacovigilance sponsor using the standard pregnancy notification form of the sponsor and the pregnancy followed to outcome.

d) Run-in Period: Those who choose to participate will be invited to give informed consent as per Good Clinical Practice standards and will be invited to enter the three month Run-In Period. They will be given a unique identifying number based on the country of origin, specific site and sequence of recruitment; this will be used for all subsequent correspondence, transfer of samples and data input. They will be encouraged to conduct frequent home blood glucose monitoring (HBGM) and record the results in a standardised Study Diary designed to record (and permit easy extraction) of changes in insulin dosages and episodes of hypoglycaemia (severe or symptomatic). Technique will be reinforced by study nurses. "Sick day rules" as in usual clinical care will be reinforced and supplemented using information printed in the Study Diary.

Individuals with higher glucose/ HbA1c concentrations at the time of enrolment will be carefully reviewed. Where possible any major changes to insulin regimen thought to be necessary at this time or during study follow-up (e.g. switch from multiple daily injections to pump therapy) will be discussed and implemented in the Run-in Period. BP control will also be reviewed in detail for each participant and any additional assessments necessary scheduled (e.g. 24 hour ambulatory BP monitoring). If these confirm that new therapy is indicated according to the above criteria, this will be discussed and explained. Where there is agreement, such therapy will be initiated (with any additional monitoring required) during the Run-in Period. Cardiovascular risk factors and cholesterol levels will be reviewed with the aim of identifying participants for whom statin therapy may be indicated at present (or in the near future). As in clinical practice, a final decision will be reached in discussion with individual participants.

It is recognised that during the years followed up in the trial many participants will require further changes to be made in their regimens in order to achieve glucose (and other) targets: such changes will be encouraged, supported and implemented.

During the third month of the Run-in Period, participants will be asked to take one tablet of run-in medication (i.e. placebo matching metformin 500 mg) once daily with their evening meal.

e) Baseline assessments: see Schedule of Assessments (page 10). At the beginning of the Run-in Period, relevant items from past medical history, concomitant medications (including duration, type and dose of any previous statin therapy) will be extracted from routine health records and validated with the participant. HbA1c, liver function tests, albuminuria and renal function results will also be captured into the electronic Case Report Form from the recent clinic visit. Where liver function tests and FBC were not performed in routine care within the previous 90 days, or where there are missing data, these will be requested from local laboratories as additional tests.

Height, body weight, ethnicity, and smoking status will be extracted where possible from routine clinic data and validated with patient. The Investigator/ study nurse will be

responsible for extracting validation information from clinical records. Adherence will be assessed by tablet counts 3-6 monthly (which will be documented on the electronic Case Report Form).

f) Randomisation visit: At the end of the three-month Run-In Period, participants will attend after avoiding strenuous exercise and having fasted from 10 pm the previous evening including avoidance of smoking and caffeine (free water intake permitted). This visit will include: (i) check of adherence to study medication over the third month (tablet counts); (ii) measurement of the primary endpoint (carotid IMT); and (iii) repeat anthropometric and metabolic assessments (see Schedule of Assessments – Section 2). Pregnancy testing will be conducted if indicated.

Participants with: (i) less than 70% adherence on tablet counts who are non-adherent in the view of site staff; or (ii) inadequate quality carotid images in the view of the local sonographer will be withdrawn at this stage i.e. before randomization. Those who met HbA1c criteria at the screening visit (R1) but who now have HbA1c < 7.0% (53 mmol/mol) will not be excluded at this visit.

Participants remaining eligible, who satisfy the study inclusion/ exclusion criteria and have provided written informed consent can then be randomized to metformin or placebo by telephone via a call to the study Interactive Voice Response System (IVRS) or electronically via the study portal for the study electronic CRF, see section 14.1.

g) Follow up: see Schedule of Assessments (page 10) and Section 10 (page 31). Participants will then have visits at one month, three months and 3-6 monthly thereafter until study cessation. As almost all patients will be attending for routine clinic care, we envisage that most visits will be conducted by study nurses in the same location and time as usual care and include:

- assessment of adherence
- capture of data on prespecified clinical events (see Section 13)
- safety questionnaire
- Diabetes Treatment Satisfaction Questionnaire
- routine clinic bloods and additional trial specific bloods
- capture of data on prespecified concurrent medications
- capture of data held in Study Diary to be used by patient to record hypoglycaemic episodes and insulin dose

h) Insulin dose titration: At the beginning of the Run-in Period, insulin regimen will be reviewed by the Investigator and optimized against standard of care [target HbA1c < 7.0% (53 mmol/L)] according to local practice under national guidelines. For example, participants may be referred into existing structured education programmes and insulin regimens may be changed e.g. from twice daily biphasic injections to multiple dose injections (MDI), or from MDI to insulin pump therapy.

Study nurses will arrange to telephone participants at 2, 4 and 8 weeks to reinforce frequent HBGM recording and monitoring, encourage hypoglycaemia reporting, discuss ongoing titration of insulin and reinforce concordance with any additional therapies prescribed. Email may be used to facilitate communication and exchange of data as an adjunct to telephone communication when convenient for participants and permitted by the relevant IRBs and Ethics Committees; however, in the UK communications of recommended changes of insulin doses will be by telephone only. Telephone visits will continue in the first four weeks following randomization with calls at 1, 2, 4 and 8 weeks between study nurse and participant during which HBGM results will be discussed.

The need to optimize glycaemic control in all participants will be emphasized at the initial Investigator Meeting and subsequent regular Investigator Teleconferences. To this end, HbA1c data, blinded to randomized therapy, will be reviewed by study centre at the University of Glasgow and fed back to Investigators three monthly with their own site performance plotted against the other sites (anonymised). Therapeutic strategies will be discussed at a teleconferences three and six months after “first-patient, first visit” and six monthly thereafter (or more frequently if required). In those centres in which average glucose control is higher than in other centres, a Steering Committee member ([name]) with particular expertise in achievement of glucose targets within trials (including DCCT and ACCORD) will lead on supporting local investigators and participants to achieve targets with every available means.

i) Hypoglycaemia management plan: Symptoms of hypoglycaemia include paleness, shaking, perspiration, a feeling of weakness, increased heart rate, hunger, agitation, difficulty in concentrating, irritability, fatigue, blurred vision, temporary loss of consciousness, confusion, convulsions and coma (see http://www.sdrm.org.uk/sites/default/files/sop27_managementofhypoglycaemia.pdf).

Participants will be asked to record all hypoglycaemic episodes on the relevant page in their Study Diary. Throughout the trial they will be encouraged to check their blood sugar if they feel hypoglycaemic and record the result. However, they should not delay treating symptoms if their blood sugar meter is not readily available. All major (severe) hypoglycaemia should be reported to the Investigator/ nurse team within 24 hours during the metformin dose titration phase of the study (see page 27 below). Contact should be maintained with the participant so that insulin dose can be adjusted appropriately. A hypoglycaemic event will be defined as “an event which causes the symptoms of hypoglycaemia at any level of blood glucose measurement or a blood glucose measurement of less than 2.8.mmol/l with or without symptoms.”

Hypoglycaemic events will be categorised into minor, major episodes and any involving unconsciousness as follows:

- **Minor episodes** are treated by the participant and will be resolved by eating some short acting glucose source, followed by a longer acting carbohydrate.
- **Major (or severe) episodes require assistance from** one or more other persons to resolve the event e.g. another family member or paramedic.
- **Major (or severe) episodes involving unconsciousness** (self-reported)

All episodes of severe hypoglycaemia should be reported to study nurses as soon as possible in order that the hypoglycaemia management plan can be followed.

As in the study by Lund et al,¹⁸ we will also record information on self-reported blood/ plasma glucose levels during hypoglycaemic events as captured from the Study Diary.

Following an episode of severe hypoglycaemia, standard causes of hypoglycaemia will be reviewed in order to identify an obvious precipitating factor (insulin dosing error, accidental intravascular injection or other injection site problem, excessive unplanned exercise, missed meal, alcohol consumption, renal impairment, loss of warning signs). HbA1c will be repeated where the most recent available value is more than six weeks previously. Where no obvious reversible precipitant is identified, participants will be advised to reduce insulin dose by 10% over the following month and perform more intensive HBGM. At review, after one month, the aim will be to uptitrate insulin dose once again, *unless* glycaemic target HbA1c < 7.0%/ 53 mmol/mol continues to be met on the reduced dose *or* there have been further episodes of major or unacceptable minor hypoglycaemia.

If the participant has a major hypoglycaemic event and is brought into the Emergency Department, this will only be considered an SAE if the hospital stay is longer than 12 hours. Minor hypoglycaemic episodes (i.e those not requiring assistance from another individual) will not be recorded as an AE.

j) Participant discontinuation: Participants will be free to discontinue study medication at any point during the study. Where possible, follow up in the trial will be continued with continuing titration of insulin doses to target. If informed consent for follow-up is withdrawn, data collected up to self-withdrawal will be included in the study unless the participant wishes otherwise. Clinical samples will be destroyed at their request.

k) Source documents: Participants will be asked to provide informed consent for investigators to obtain copies of official documentation (discharge letter or clinic letter) of any cardiovascular events which will be made available at the request of study monitors. This will also apply for Severe Adverse Event reporting (Section 13, page 34 for which we will obtain copies of official documentation (discharge letter or clinic letter).

l) Long term follow-up: Informed consent will be sought from participants for later long-term follow-up for events occurring following completion of the trial via linkage to national databases (e.g. cardiovascular events/ mortality). Where permitted by ethics/ IRB committees in the various national territories, consent will also be sought for up to 20 years for: (i) contacting the participant's primary care practitioner; (ii) contacting by telephone to complete questionnaire(s); (iii) sending out questionnaire(s); and/or (iv) inviting to follow-up visit(s).

